3.3.2 Periodontal Treatment Protocol

Periodontal treatment was performed by a trained periodontist using a standardized quadrant approach, with half-mouth treatments completed per session separated by one-week intervals to ensure patient comfort and procedural consistency. Both treatment groups received full-mouth scaling and root planing using an EMS AIR-FLOW MASTER PIEZON® ultrasonic scaler and Gracey curettes, followed by comprehensive oral hygiene instructions and scheduling for 3-month follow-up visits.

The experimental group additionally received immediate Nd:YAG laser therapy post-SRP using a Wiser Waterlase MD system (Vista Dental) with manufacturer-recommended settings (150mJ/pulse, 20Hz frequency, water level 1 and air level 3 coolant). The laser was applied in a continuous zig-zag pattern across root surfaces and pocket linings, maintaining a 30° angle and delivering 2-second irradiation per treatment site to ensure thorough antimicrobial coverage while minimizing thermal damage to surrounding tissues.

All procedures were conducted under local anesthesia when clinically indicated, with strict adherence to infection control protocols and standardized patient positioning. Treatment fidelity was maintained through operator calibration, use of timer-controlled laser application, and periodic quality assurance checks to ensure consistent intervention delivery across all study participants throughout the trial duration.

3.3.3 Subgingival Plaque Sampling and Microbiome Analysis

Subgingival plaque sampling procedure: Subgingival plaque samples were collected from six designated teeth (#16, #21, #24, #36, #41, #44) at baseline and 3-month follow-up, with adjacent

teeth substituted if target teeth were missing. After isolation with sterile cotton rolls and removal of supragingival plaque, subgingival plaque was obtained using sterile Gracey curettes and immediately placed in 1.5 mL sterile microtubes containing phosphate-buffered saline (PBS). All samples were stored at -80°C until analysis. The collected samples were subsequently sent to MajorBio Corporation for 16S rDNA high-throughput sequencing (V3-V4 hypervariable regions, Illumina platform). Bioinformatic analysis was performed using QIIME2 pipeline with SILVA 138 database for taxonomic classification. The sequencing results were then integrated with clinical parameters for comprehensive cross-sectional and longitudinal analyses to evaluate microbial shifts following treatment.

3.4 Data Management and Statistical Analysis Plan

Data collection and entry were performed according to standardized operating procedures (SOPs), with researchers manually entering all study data into a unified Excel spreadsheet.

Statistical analyses were conducted using SPSS 25.0 software. For continuous variables, the Shapiro-Wilk test was employed to assess normality of distribution. Normally distributed measurement data were expressed as mean \pm standard deviation (SD), with between-group comparisons analyzed using independent samples t-tests and within-group pre-post treatment comparisons evaluated with paired t-tests. Categorical data were presented as percentages (%) and compared using chi-square tests. A two-sided P-value < 0.05 was considered statistically significant for all analyses.

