3.2 Sample Size Calculation

Based on preliminary data, the mean difference in post-treatment probing depth (PD) between the SRP group and Nd:YAG-assisted SRP group was estimated at 0.45 mm, with a standard deviation (SD) of 0.58 mm. Using PASS 25.0 software, we calculated the required sample size with the following parameters: Significance level (α): 0.05 (two-tailed) and Power (1- β): 90%. The initial computation indicated a minimum of 18 participants per group. To account for a potential $\leq 20\%$ dropout rate, the final sample size was adjusted to at least 23 subjects per group (46 total).

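### Section 3.4 lets a Shapiro-Wilk result decide whether an outcome keeps its mean-difference analysis, including the PD difference on which the trial was sized

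*Protocol*

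**What the plan says.** Protocol section 3.4 sets a check on continuous data first: "the Shapiro-Wilk test was employed to assess normality of distribution". The next sentence is limited to measurement data that are normally distributed. For those it specifies mean and SD, "with between-group comparisons analyzed using independent samples t-tests and within-group pre-post treatment comparisons evaluated with paired t-tests". It names no other summary or test for continuous data. It does not say whether the check is made per arm, on pooled data or on changes, or at which visit. It gives no level for the check beyond the general statement "A two-sided P-value < 0.05 was considered statistically significant for all analyses".

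Section 3.2 bases the sample size on "the mean difference in post-treatment probing depth (PD) between the SRP group" and the laser-assisted group, which "was estimated at 0.45 mm, with a standard deviation (SD) of 0.58 mm". The quantity the trial was designed to estimate is therefore a difference in means, in mm.

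Section 3.3.1 makes every clinical outcome (PD, CAL, GI, PI, BOP) a patient-level mean over six sites per tooth, measured at baseline and 3 months. Section 3.1 gives arm sizes of 62 and 63.

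**The concern.** A normality pre-test asks whether the patient values come from a normal distribution. The two-sample t-test needs something weaker, namely that the difference in arm means is approximately normal, and with about 60 patients per arm moderate skew does not prevent that. The power of Shapiro-Wilk to detect skew rises with sample size, while the consequence of skew for the t-test falls. At these arm sizes the check can therefore set aside the planned analysis for a departure that does not matter.

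The mean PD difference is what section 3.2 was written to detect. If PD fails, the one between-group comparison that section 3.4 states for continuous data no longer applies to it, and this protocol does not say what replaces it. The unit and time point of the check are also open, so the pass or fail decision itself leaves room for choice. PD and CAL, both in mm, could end up reported in different ways, one as a mean difference and the other by some rank-based summary.

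**Working it through.** **The plan's own figure.** The only related figure is the sample size, set with "Significance level (α): 0.05 (two-tailed) and Power (1- β): 90"%. The two-sample formula is n = 2(1.960 + 1.282)² / (0.45/0.58)². It gives 35 per group (36 with the t distribution), not the stated 18. The dropout step is correct: 18/0.8 = 22.5, so 23. The 18 is a separate matter on which this point does not depend, so both the planned 23 per group and the reported 62 and 63 are examined below.

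**Inputs from the protocol.** Arm sizes are 62 and 63 (3.1), the planned size is 23 per group (3.2), the difference is 0.45 mm with SD 0.58 mm (3.2), and the level is 0.05 two-sided (3.4).

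**Assumptions, because the documents are silent.** Shapiro-Wilk is applied to each arm at 0.05, and an outcome fails if either arm fails. PD patient means are lognormal with a given skewness. Where a fallback is needed, Mann-Whitney is used.

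**Step 1: how often PD at 3 months fails.** With a per-arm rejection rate r, the chance that at least one of two arms fails is 1 − (1 − r)². Simulated per-arm rates at n = 62 are 13%, 37% and 68% at skewness 0.30, 0.61 and 0.95. With normal data the rate is 5% by construction.

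- Normal: 1 − 0.95² = 0.10
- Skewness 0.30: 1 − 0.87² = 0.24
- Skewness 0.61: 1 − 0.63² = 0.60
- Skewness 0.95: 1 − 0.32² = 0.90

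Direct two-arm simulation agrees:

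| Assumed skewness | Fails in at least one arm, 62/63 | Fails in at least one arm, 23/23 |
|---|---|---|
| 0 (normal) | about 10% | about 9% |
| 0.3 | about 25% | about 15% |
| 0.6 | about 60% | about 28% |
| 0.95 | about 90% | about 48% |

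Gamma data give the same picture at 62/63: 47%, 74% and 96% at skewness 0.5, 0.7 and 1.0. At 23/23 the figures are 22%, 34% and 56%.

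**Step 2: does that skew harm the t-test?** Type I error of the t-test without the pre-test at 62/63 is 4.8% to 5.6% over lognormal skewness 0.30 to 1.32 (8,000 runs). Over gamma skewness 0 to 1.5 it is 4.7% to 5.3% (10,000 runs). At 23/23 with gamma data it is 4.9% to 5.3%. Power for 0.45 mm at 62/63 is about 99% throughout. The t-test does not need the protection.

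**Step 3: does the two-stage rule itself do harm?** With Mann-Whitney as the assumed fallback, type I error at 62/63 is 4.2% to 5.4% with lognormal data and 4.9% to 5.5% with gamma data. It is at most 5.6% in any gamma scenario, including smaller arms. Power at 62/63 is also about 99%. Error rates are essentially the same with or without the pre-test. What changes is which quantity is estimated and reported.

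**The case against.** The strongest reply has three parts.

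*A separate SAP may name the method for variables that fail.* This is fair. A protocol often leaves that detail out, and its absence is not the fault alleged here. A reader might infer that failing variables go uncompared, or that a substitute will certainly be picked after the data are seen. The protocol says neither. A named fallback would close off the free choice of test. It would not remove the rule in section 3.4 that makes the planned mean difference conditional on a pre-test.

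*No inferential damage follows.* This stands. A reader might infer that testing in two stages inflates false positives, but step 3 shows error near 5%. Among trials that pass the check at gamma skewness 1.0, t-test error is about 7%. Only 4% of trials pass there (100% − 96%), and the error of the whole rule stays near 5%.

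*The failure rates are assumed.* This also stands. At skewness 0.3 the rate is about 25%, and at 23 per group all the skewed-data rates are lower. It is also tempting to count 5 indices × 2 arms × 2 visits = 20 checks and quote 1 − 0.95²⁰ = 64% for at least one failure in normal data. That treats correlated indices, measured twice on the same patients, as independent. It also says nothing about PD, for which the figure is about 10%. Nor can all five outcomes lose a difference in mm, because only PD and CAL are in mm.

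**Conclusion.** The point holds in a limited form. Section 3.4 makes the stated analysis of each continuous outcome depend on Shapiro-Wilk, and for PD that puts at risk the mean difference on which the trial was sized. At 62/63 the pre-test would set aside the t-test for PD in roughly 10% to 90% of trials over skewness 0 to 0.95, and at 23 per group in roughly 9% to 48%. The t-test needs no such protection at either size. These rates rest on assumed lognormal data, per-arm testing and a 0.05 level, none of which the protocol fixes for the check.

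The harm is loss of the prespecified estimate and more analytic freedom. The documents do not support a claim of inflated error or lost power. The change is worth making because it is nearly free; the point is minor to moderate in weight.

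**What to change.** In section 3.4, stop using Shapiro-Wilk to choose the analysis of the patient-mean clinical indices. State that, whatever its result, the 3-month patient means will be compared between arms with a linear model that has the patient's baseline mean as covariate. Report the adjusted difference with its 95% CI: mm for PD and CAL, index units or percentage for GI, PI and BOP. Name a rank-based test as a sensitivity analysis.

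Fixing the mean-difference comparison in advance is what cures the defect. The baseline covariate is an improvement that uses values already collected under section 3.3.1. The cost is a wording change and slightly more analysis, with no new data.

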Research Protocol

Project Name: Characteristics of Subgingival Microbiota in Patients with Stage III-IV Periodontitis in Response to Nd:YAG Laser-Assisted Therapy

August 16, 2024

1. Research Background and Rationale

Periodontitis is a microbially associated, host-mediated chronic inflammatory disease. Stage III-IV periodontitis, representing the advanced phase of disease progression, is characterized by severe alveolar bone loss and irreversible clinical attachment loss (CAL). According to the latest Global Burden of Disease Study, periodontitis ranks as the sixth most prevalent condition globally, with Stage III-IV cases constituting a significant proportion of affected individuals^[1].

The primary therapeutic objectives in periodontitis management are plaque control and inflammation resolution. Conventional scaling and root planing (SRP), while foundational, exhibits inherent limitations including incomplete biofilm removal and iatrogenic tissue trauma^[2]. The neodymium-doped yttrium-aluminium-garnet (Nd:YAG) laser (wavelength: 1064 nm), a near-infrared laser modality, demonstrates selective absorption for melanin and hemoglobin while maintaining low water absorption coefficients (0.61 cm^{-1}). This unique photophysical property enables deep tissue penetration and localized photothermal effects^[3]. Recognized for its potent bactericidal, hemostatic, and soft tissue ablation capabilities, Nd:YAG laser has emerged as a minimally invasive adjunct to periodontal therapy. Nevertheless, the response patterns of subgingival microbiomes to Nd:YAG laser-assisted treatment remain insufficiently characterized in the current literature.

2. Study Objectives

This study aims to comparatively evaluate the clinical efficacy of Nd:YAG laser-assisted scaling and root planing (SRP) versus conventional SRP alone in the treatment of stage III-IV periodontitis. Furthermore, we seek to investigate the effects of Nd:YAG laser adjunctive therapy on the compositional structure and diversity of subgingival microbiota. By elucidating the potential

role of Nd:YAG laser in modulating subgingival microbial equilibrium, this research will provide novel theoretical insights and evidence-based guidance for the clinical management of periodontitis.

3. Study Design

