3.1 Study Setting and Participants

From August 2024 to March 2025, 120 patients with stage III-IV periodontitis were recruited from the Department of Stomatology, The First Affiliated Hospital of Sun Yat-sen University, according to predefined eligibility criteria. All participants provided written informed consent. The study subjects were randomly allocated to either the conventional subgingival scaling and root planing (SRP) group (n=62) or the Nd:YAG laser-assisted SRP group (n=63).

3.1.1 Inclusion Criteria (1) Diagnosis of stage III-IV periodontitis based on the 2018 classification system jointly proposed by the European Federation of Periodontology (EFP) and the American Academy of Periodontology (AAP)^[4, 5], with: Maximum interdental clinical attachment loss (CAL) ≥ 5 mm, and Radiographic bone loss extending to the mid-third of the root or beyond; (2) Age 18–80 years; (3) Minimum of 14 natural teeth remaining in the dentition; (4) Willingness to provide informed consent and comply with study protocols.

3.1.2 Exclusion Criteria (1) Systemic conditions affecting periodontal treatment outcomes; (2) Periodontal therapy within the past 6 months; (3) Recent use of antibiotics or medications associated with gingival enlargement; (4) Pregnancy or lactation; (5) Acute periodontal lesions; (6) Inability to cooperate.

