3.3 Study Procedures

3.3.1 Periodontal Examination

One week after supragingival scaling, a single-blinded periodontist performed full-mouth examinations at baseline and 3-month follow-up, following the WHO Oral Health Surveys Basic Methods guidelines^[6]. For each tooth, six sites (mesiobuccal, midbuccal, distobuccal, mesiolingual, midlingual, distolingual) were assessed for probing depth (PD), clinical attachment loss (CAL), gingival index (GI), plaque index (PI) and bleeding on probing (BOP). The mean value of each parameter per patient was recorded as the final measurement.

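### Section 3.4 compares the arms by t-test without the baseline value every patient has; for 3-month values, adjusting for it narrows the interval unless the baseline/3-month correlation is near zero

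*Protocol*

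**What the plan says.** Protocol Section 3.4 fixes the method for normally distributed measurements: "between-group comparisons analyzed using independent samples t-tests". Normality is screened beforehand: "the Shapiro-Wilk test was employed to assess normality of distribution". Baseline enters only through paired t-tests within each arm, and these do not estimate the difference between arms. No regression model or covariate appears anywhere in the protocol.

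Section 3.3.1 shows that the covariate exists. A periodontist "performed full-mouth examinations at baseline and 3-month follow-up" for PD, CAL, GI, PI and BOP, and "The mean value of each parameter per patient was recorded as the final measurement". Each patient therefore has one baseline and one 3-month value for each parameter.

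Section 3.4 does not say whether the t-test is applied to 3-month values or to changes. Section 3.2 points to 3-month values, because it sizes the trial on "the mean difference in post-treatment probing depth (PD) between the SRP group and Nd:YAG-assisted SRP group", "estimated at 0.45 mm, with a standard deviation (SD) of 0.58 mm".

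**The concern.** The first aim in Section 2 is to "comparatively evaluate the clinical efficacy of Nd:YAG laser-assisted scaling and root planing (SRP) versus conventional SRP alone". The main clinical result is therefore the laser-minus-SRP difference and its interval. A patient's baseline value of a periodontal measure may well predict that patient's 3-month value. If it does, a t-test on 3-month values leaves explainable variation between patients in the error term, and a t-test on change subtracts baseline with a coefficient fixed at 1, whatever the data support. ANCOVA estimates that coefficient.

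Bias and type I error are not at issue. What is at stake is an interval wider than the collected data require, and a result that depends on which of two unstated t-tests is run.

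**Working it through.** **Inputs from the protocol.** Difference 0.45 mm, SD 0.58 mm, two-sided α 0.05, 90% power, 18 per group (23 after dropout) (Section 3.2); allocation "group (n=62) or the Nd:YAG laser-assisted SRP group (n=63") (Section 3.1).

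**Assumptions not in the protocol.** r = 0.3, 0.5 or 0.7; 0.58 mm is the between-patient SD at both visits. Only PD can be put in mm, because no SD is given for the other parameters.

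**The plan's own figure.** The two-sample normal formula gives 2 × [0.58 × (1.960 + 1.282)/0.45]² = 34.9, so 35 per group (36 with the t distribution), not 18. The value 18 is what the one-sample or paired normal formula gives (17.5, rounded up). That is a separate defect and the present point does not rest on it.

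**Step 1: t-test on 3-month values, 62/63.**
- k = √(1/62 + 1/63) = 0.1789
- SE = 0.58 × k = 0.1038 mm
- Half-width = t(0.975; 123 df) × SE = 0.205 mm

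**Step 2: the alternatives, 62/63.** ANCOVA SE = 0.58 × √(1 − r²) × k, with 122 df. Change-score SE with equal SDs = 0.58 × √(2(1 − r)) × k, with 123 df.

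| | r = 0.3 | r = 0.5 | r = 0.7 |
|---|---|---|---|
| Half-width, 3-month t-test (mm) | 0.205 | 0.205 | 0.205 |
| Half-width, change t-test (mm) | 0.243 | 0.205 | 0.159 |
| Half-width, ANCOVA (mm) | 0.196 | 0.178 | 0.147 |
| ANCOVA narrower than 3-month t-test | 4% | 13% | 28% |
| Variance ratio to 3-month value, 1 − r² | 0.91 | 0.75 | 0.51 |
| Same × (1 + 1/(N − 4)), cost of estimating the slope | 0.918 | 0.756 | 0.514 |

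With the slope cost included, the ANCOVA half-widths are 0.197, 0.179 and 0.147 mm, and the percentages do not change. Simulation (40,000 runs) gave mean half-widths of 0.196, 0.178 and 0.147 mm. At r = 0.5 it gave type I error of 0.051 (3-month), 0.050 (change) and 0.051 (ANCOVA).

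**Step 3: when adjustment does not help against 3-month values.** Break-even solves t(N − 3) × √[(1 − r²)(1 + 1/(N − 4))] = t(N − 2). This gives |r| = 0.091 at N = 125 and 0.157 at N = 46. At r = 0 the ANCOVA half-width is larger by a factor of 1.004 and 1.012 respectively.

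**Step 4: against change scores.** With q = baseline SD / 3-month SD, the variance ratio ANCOVA/change is (1 − r²)/(1 + q² − 2rq), before the slope cost.

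| q | r = 0.3 | r = 0.5 | r = 0.7 |
|---|---|---|---|
| 1 | 0.65 | 0.75 | 0.85 |
| 1.5 | 0.387 | 0.429 | 0.443 |
| 2/3 | 0.871 | 0.964 | 0.998 |

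In the last cell the slope cost tips the balance: 0.998 × (1 + 1/121) = 1.006, so the ANCOVA half-width is about 0.3% wider. With equal SDs, break-even is r = 0.98 at N = 125 and 0.95 at N = 46.

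**Step 5: power for 0.45 mm (noncentral t).**

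| | 3-month | Change (r = 0.3, 0.5, 0.7) | ANCOVA (r = 0.3, 0.5, 0.7) |
|---|---|---|---|
| 62/63 | 0.990 | 0.953, 0.990, 0.9998 | 0.994, 0.999, >0.999 |
| 23/23 | 0.730 | 0.585, 0.730, 0.913 | 0.760, 0.835, 0.945 |

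**Step 6: a realised baseline imbalance.** An imbalance b of one SE (0.104 mm) moves the expected 3-month difference by r × b, or 0.031 to 0.073 mm over r = 0.3 to 0.7. It moves the change difference by −(1 − r) × b, or −0.073 to −0.031 mm. Over repeated randomisation this is already inside the t-test's SE, so it illustrates the same loss and does not add to it.

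**The case against.** The strongest reply is that nothing here is wrong: the t-test is valid, and at 62/63 it already has 99% power for the planned difference. That stands, and it limits the point to a precision gain.

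The size of that gain also rests on a correlation the protocol does not supply. At r = 0.3 it is only about 0.009 mm, and the 28% figure needs r = 0.7. This stands too. The direction does not depend on a particular r, however, because the break-even is about 0.09 and the worst-case loss about 0.4%.

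The near-zero condition applies to a t-test on 3-month values. Section 3.2 implies that outcome, but Section 3.4 does not state it. Against change, ANCOVA can lose slightly when the baseline SD is the smaller one (Step 4), though within the same worst case.

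The power gains at 23 per group belong to a planned minimum that the reported allocation exceeds, and should carry little weight.

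The mm figures treat all 125 as analysed, whereas Section 3.1 also gives 120 recruited and Section 3.2 allows up to 20% dropout. With 50 per arm the unadjusted half-width is about 0.230 mm and power 97%. The ratio √[(1 − r²)(1 + 1/96)] is then 0.959, 0.870 and 0.718, so the percentage gain is essentially the same.

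**Conclusion.** The concern holds, as a point of precision. The protocol fixes an unadjusted comparison although the baseline of the same measure is available for each clinical parameter. For PD at 62/63, adjustment would narrow the 95% interval by about 4%, 13% or 28% at r = 0.3, 0.5 or 0.7, against a worst case of about 0.4% wider. The percentages against 3-month values depend almost entirely on r. The mm values also need 0.58 mm to be the between-patient SD at 3 months and nearly all allocated patients to be analysed. Against a t-test on change, the gain depends on the ratio of the two SDs as well, from about nil to a variance reduction of about 61% over the range shown. The planned test is not invalid and, at the reported allocation, not underpowered for 0.45 mm. The change is worth making because it costs almost nothing and also settles whether 3-month values or changes are compared.

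**What to change.** In Section 3.4, replace the between-group t-test for continuous clinical parameters by a linear model of the 3-month value on treatment arm and the baseline value of the same parameter. Report the adjusted laser-minus-SRP difference with its 95% interval as the treatment comparison. Judge normality on the model residuals instead of by Shapiro-Wilk on raw values, and say what will be done if they are clearly unsuitable.

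Date the change. The protocol is written in the past tense, so state whether outcome data had been seen. If they had, the adjusted model is post hoc: show the unadjusted t-test beside it and say whether that test uses the 3-month value or the change.

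The cost is a few sentences, one residual degree of freedom and an assumed linear relation to baseline. No new data are needed, and SPSS, which the protocol already names, fits the model.

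### Section 3.4 applies one P < 0.05 threshold to every analysis and the 16S data get no other rule; read literally and applied taxon by taxon without adjustment, it would call a nominal 5% of unaffected taxa significant

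*Protocol*

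**What the plan says.** Section 3.4, which carries the analysis plan in its title, names its software ("Statistical analyses were conducted using SPSS 25.0 software"), a normality check, independent-samples t-tests between groups, "within-group pre-post treatment comparisons evaluated with paired t-tests", and chi-square tests for categorical data. It closes with the only significance rule in the protocol: "A two-sided P-value < 0.05 was considered statistically significant for all analyses".

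The microbiota work is described elsewhere. Section 2 makes the "effects of Nd:YAG laser adjunctive therapy on the compositional structure and diversity of subgingival microbiota" an objective. Section 3.3.3 says "Bioinformatic analysis was performed using QIIME2 pipeline with SILVA 138 database for taxonomic classification", and that the results feed into "comprehensive cross-sectional and longitudinal analyses to evaluate microbial shifts following treatment". It names no test, error rate or adjustment for taxa. The protocol does not say how many taxa are expected, or at which taxonomic level they would be compared.

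**The concern.** A 0.05 threshold suits a handful of comparisons. Sequencing data classified into taxa can produce tens or hundreds. If the universal threshold is used for each taxon on raw P-values, the number of chance findings grows in proportion to the number of unaffected taxa tested. Sections 3.3.3 and 3.4 together suggest up to three comparison sets: between groups, and before versus after treatment within each arm.

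The microbiota response is the subject of the title and the second objective. A published list of laser-responsive taxa is the likely product, and a reader of such a list could not tell true shifts from chance hits. Overall comparisons of diversity or community composition are few, so they are affected much less.

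**Working it through.** **Inputs from the protocol.** Threshold: two-sided 0.05 (section 3.4). Arm sizes: 62 and 63 (section 3.1, which also gives a total of 120; the stated arm sizes are used here). Dropout allowance: up to 20% (section 3.2).

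**Inputs assumed.** The number of taxa m, the number truly shifted and the size of the shift are not in the protocol. Everything below that depends on them is illustrative.

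**Step 1: expected false calls.** The protocol gives no figure of its own to reproduce here, only the threshold. With no taxon affected, expected false calls per comparison set = 0.05 × m:
- m = 20: 1
- m = 50: 2.5
- m = 100: 5
- m = 200: 10

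Correlation between taxa does not change these expectations, provided each test holds its nominal level. A simulated null (200 taxa, 62 versus 63, normal data) flagged 5.0%. The 5% is nominal: in one assumed sparse, skewed null (30% prevalence, lognormal values) the plain t-test flagged about 2%.

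**Step 2: few taxa shift (between groups).** Take m = 100 with 5 taxa shifted by 0.5 SD, 62 versus 63.
- False calls: 0.05 × 95 = 4.75.
- Power per shifted taxon: noncentrality = 0.5 × √(62 × 63 / 125) = 2.79, critical t = 1.98, power = 0.79. True calls: 5 × 0.79 = 3.96.
- Ratio of expectations: 4.75 / (4.75 + 3.96) = 0.55. The mean share over 20,000 simulated draws with independent t statistics is 0.52.
- Benjamini-Hochberg at 5%: 1.5 true calls, mean false share just under 0.05.

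Other cases, same method:

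| Patients | Shifted | Shift | True, raw | Mean false share, raw | True, BH | Mean false share, BH |
|---|---|---|---|---|---|---|
| 62 vs 63 | 5 of 100 | 0.8 SD | 4.97 | 0.46 | 4.56 | 0.048 |
| 50 vs 50 | 5 of 100 | 0.5 SD | 3.50 | 0.56 | 0.95 | 0.046 |
| 50 vs 50 | 5 of 20 | 0.8 SD | – | 0.12 | – | 0.037 |

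The 50 versus 50 rows apply the full 20% loss: 62 × 0.8 = 49.6 and 63 × 0.8 = 50.4.

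**Step 3: many taxa shift.** Both arms receive scaling and root planing (section 3.3.2), so changes from before to after treatment may be widespread. Take m = 100 with 50 taxa shifted by 0.8 SD, 62 versus 63, using the two-sample calculation as a stand-in for a paired one.
- False calls: 0.05 × 50 = 2.5.
- Power 0.99, so true calls are about 49.7.
- False share: 2.5 / 52.2 = 0.048.

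**Step 4: community-level comparisons.** For 3 to 5 independent indices with no effect, expected false calls are 0.15 to 0.25. The chance of at least one is 1 − 0.95³ = 0.14 to 1 − 0.95⁵ = 0.23.

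**The case against.** The strongest reply is that this is a detail for a statistical analysis plan that is not at hand, and that the sentence in section 3.4 is not wrong. It does not say whether P-values are raw or adjusted, and a Benjamini-Hochberg rule could be applied without contradicting it. It closes a paragraph on SPSS, t-tests and chi-square tests, while the sequencing work sits in another section under another software pipeline. The objective speaks of composition and diversity, and diversity is a community-level measure. The t-tests are tied to normally distributed data, which taxon abundances often are not.

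Much of this stands. A reader might infer that the protocol commits to screening taxa individually on raw P-values. It does not say so: the taxonomic classification and the aim of evaluating shifts imply taxon-wise comparison, but no sentence states it. The false-call count is therefore conditional on two things that are not written down.

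What does not stand is that nothing is fixed. Section 3.4 chose universal scope for its threshold, and no other section gives the sequencing data a different one. A later plan that controls false discoveries would have to depart from that sentence or explain it. Under the narrower reading, the protocol has no decision rule at all for its titular outcome, and the same short clarification resolves both readings.

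It is also fair that adjustment costs detections and that the microbiota objective is nowhere called confirmatory. That bears on how the trade-off is judged, and the cost is stated under the fix.

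**Conclusion.** The point holds as a conditional one and is worth considering; confidence is medium. Read literally and applied to taxa individually with unadjusted P-values, the rule in section 3.4 calls a nominal 5% of unaffected taxa significant in each comparison set. That rate assumes tests that hold their level; sparse, skewed abundances may give less.

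A reader might go further and infer that about half of the taxa reported by this trial will be false, or that the illustrated shares bracket the truth. The protocol supports neither. About half is what follows between groups if few taxa shift (52% with 5 of 100 shifted by 0.5 SD). About 5% is what follows if half of 100 taxa shift by 0.8 SD. The answer depends on taxon counts and effects that the protocol does not give, and the calculations treat taxa as independent.

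**What to change.** In section 3.4, limit the unadjusted two-sided 0.05 threshold to the clinical parameters and the few community-level comparisons (diversity indices, overall composition). Add that taxon-level comparisons are judged on Benjamini-Hochberg adjusted P-values at a 5% false discovery rate within each comparison set: between groups, and pre-post within each arm. If a separate analysis plan already says this, a cross-reference in section 3.4 is enough.

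The cost is one or two sentences and minor analysis work, with no new data. Fewer taxa will be called significant, mainly those with small shifts. With 5 of 100 taxa shifted and 62 versus 63 patients, true detections fall from 4.0 to 1.5 at 0.5 SD, but only from 5.0 to 4.6 at 0.8 SD. Leaving the community-level comparisons unadjusted accepts the 14% to 23% chance of at least one false call worked out above.
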